7.2.2 Timepoint 2: At 8 weeks post-partum

8 weeks following delivery, patients’ medical records will be reviewed to assess continued eligibility. Eligible participants will receive an automated electronic mail message with a link to the questionnaire to be completed on REDCap. There is not a required office visit for this timepoint. If the questionnaire is not completed within one week, another reminder message with a link to the REDCap questionnaire will be sent via electronic mail. These results will be stored under the REDCap database.

7.2.3 Timepoint 3: At 6 months post-partum

6 months following delivery, those participants who were eligible at 8 weeks postpartum will receive an automated electronic mail message with a link to the questionnaire to be completed on REDCap. There is not a required office visit for this timepoint. If the questionnaire is not completed within one week, another reminder message with a link to the REDCap questionnaire will be sent via electronic mail. These results will be stored under the REDCap database.

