3.3 Early Withdrawal of Subjects

3.3.1 Criteria for removal from study

Patients will be withdrawn from the study should they deliver prior to 34 0/7 weeks gestational age or have a fetal demise, postpartum course complicated by an ICU stay, or receive an emergency hysterectomy at delivery. Patients will also be withdrawn if they fail to complete key components of the intake survey (i.e. name, date of birth, email address, or obstetric history) or the 8-week postpartum survey. Patients will be contacted by email and/or telephone. Should a patient fail to respond to these attempts at contact, they will be presumed to have withdrawn from the study. Additionally, any patient can withdraw from the study at any point upon their request. As this is a low-risk trial, we do not anticipate any patients being withdrawn for safety reasons or adverse health outcomes.

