3.3.2 Follow-up for withdrawn subjects

At any point upon subject request or upon failure to complete surveys, patients will be withdrawn from the study. No further data will be collected on withdrawn subjects, and there will be no additional follow-up beyond the postpartum standard of care. Following the withdrawal of a subject, that individual will not be replaced in this study.

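### The plan does not settle whether a woman who misses the 8-week survey is sent the 6-month survey; if Section 3.3 governs, the 6-month endpoint covers only 8-week responders

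*Combined protocol and SAP*

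**What the plan says.** Two parts of the protocol decide who is followed to 6 months.

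- **Study procedures.** At 8 weeks, "medical records will be reviewed to assess continued eligibility" (Section 7.2.2). The survey follows that check: "Eligible participants will receive an automated electronic mail message with a link to the questionnaire to be completed on REDCap". Section 7.2.3 then uses the same status for the later mailing: "those participants who were eligible at 8 weeks postpartum will receive an automated electronic mail message with a link to the questionnaire". It does not require an 8-week answer.
- **Withdrawal rules.** Section 3.3.1 removes women who "fail to complete key components of the intake survey" "or the 8-week postpartum survey". On unanswered contact it adds: "Should a patient fail to respond to these attempts at contact, they will be presumed to have withdrawn from the study". Section 3.3.2 repeats that "upon failure to complete surveys, patients will be withdrawn from the study" and continues: "No further data will be collected on withdrawn subjects".

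Contraception use at 6 months is a secondary endpoint (Section 1.3). Sections 1.1 and 7.3 describe assessment at both times with no condition on the first survey. Section 13.0 ties the gift card to completing all three surveys. Section 8.3 specifies an analysis for the 8-week comparison only.

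**The concern.** For a woman who passes the chart review but does not answer at 8 weeks, Section 7.2.3 read literally sends a 6-month survey, while Section 3.3 ends data collection. The automated send rule must follow one or the other, and the plan does not say which.

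The choice affects the randomised comparison. Answering at 8 weeks happens after randomisation and after the handout has been given. If it becomes the entry ticket for 6-month follow-up, the arms compared at 6 months are 8-week responders and not the women randomised. Nothing about the 6-month outcome requires this, since current contraception use can be reported without an 8-week answer. An outcome that was never requested cannot be recovered by any later analysis.

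**Working it through.** **1. The texts side by side, for a woman eligible on chart review who does not answer at 8 weeks**

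| Section | Consequence for her |
|---|---|
| 7.2.2 | Eligible; status fixed before the survey is sent |
| 7.2.3 | Sent the 6-month survey |
| 3.3.1 | Withdrawn, or presumed withdrawn after failed contact |
| 3.3.2 | Withdrawn; no further data |

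No section ranks these rules.

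**2. The plan's own sample size**

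Inputs (Sections 8.1 and 8.2): 0.75 versus 0.90, two-sided alpha 0.05, 80% power, 10% drop-out. With n per arm and mean proportion 0.825:

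power = Φ{[0.15√n − 1.96√(2 × 0.825 × 0.175)] / √(0.75 × 0.25 + 0.90 × 0.10)} = Φ{[0.15√n − 1.0532] / 0.5268}

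At n = 100: (1.5000 − 1.0532)/0.5268 = 0.848, power 80.2%. Drop-out: 100/0.9 = 111.1, rounded up to 112 per arm, 224 in total. The plan's figures reproduce.

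**3. How many women are affected at the plan's drop-out**

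- 224 × 0.10 = 22.4, about 22 women. Given the 10%, this is a ceiling, because that figure also covers clinical removals and later loss.
- If Section 3.3 governs and all 22 are 8-week non-responders: 224 − 22 = 202 women at 6 months.
- If Section 7.2.3 governs and 10-50% of the 22 answer at 6 months (assumed): 22 × 0.10 = 2 and 22 × 0.50 = 11, giving 204 to 213 women.

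**4. Power and precision at 6 months**

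No 6-month rates are given, so the 8-week planning rates stand in, with equal arms.

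| Women in total | Per arm | Argument of Φ | Power |
|---|---|---|---|
| 202 | 101 | 0.862 | 80.6% |
| 204 | 102 | 0.877 | 81.0% |
| 213 | 106.5 | 0.939 | 82.6% |

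The gain is 0.4 to 2.0 percentage points. The 95% confidence interval half-width for the difference is 1.96√(0.2775/n), where 0.2775 = 0.1875 + 0.0900: 10.3 points at 101 per arm and 10.0 at 106.5.

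**5. If 8-week non-response exceeds the plan's figure**

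These inputs are assumptions: 8-week response 70-90%, 6-month response among 8-week responders 80-90%, and 25-50% of 8-week non-responders answering at 6 months.

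- Section 3.3 governs: from 224 × 0.7 × 0.8 = 125 to 224 × 0.9 × 0.9 = 181 women; power about 60-76%.
- Section 7.2.3 governs: from 125.4 + 224 × 0.3 × 0.25 = 142 to 181.4 + 224 × 0.1 × 0.50 = 193 women; power about 66-79%.

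**6. Bias**

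No figure can be derived. It would require 8-week response, or its link with contraception use, to differ by arm, and the documents contain no response data by arm.

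**The case against.** The strongest reply is that the sections can be read together. Section 3.3.2 is categorical, a withdrawn woman is arguably no longer a participant, and Section 7.2.3 speaks of participants. The gift card rule in Section 13.0 fits this reading, as does the statement in Section 7.3 that the 8-week questionnaire is the primary endpoint for participation. Sections 1.1 and 7.3 are short overviews that also leave out the clinical removals, so their silence is weak evidence for a competing rule. On this view following only 8-week completers is a stated design choice, on a secondary endpoint with no planned test and little effect on power.

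The harmonised reading is fair, but it does not rescue the plan. It makes the restriction to 8-week responders certain, with nothing gained in return.

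Some of the objection stands. The numerical size is illustrative: the recovery rate is assumed, and the 202 figure assigns the whole 10% to 8-week non-response, so recovering some of those women takes total loss below 10%. The removal criterion can also be read as covering key components of the 8-week survey, which leaves partial completers unclear. None of this changes the conclusion.

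**Conclusion.** The concern holds, and the plan should be changed. Either Sections 3.3 and 7.2.3 give opposite instructions for an eligible 8-week non-responder, or they agree in limiting a secondary endpoint to women selected by a post-randomisation response.

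The loss of power is small if the plan's 10% drop-out holds and would grow with heavier 8-week non-response. The main reasons to act are to keep 6-month follow-up as close as possible to the randomised groups and to remove an unresolved instruction. The primary endpoint and its sample size are not affected. Confidence is medium, because the sections can be harmonised and the documents report no response rates.

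**What to change.** - In Sections 3.3.1, 3.3.2 and 7.2.3, state that a missed 8-week survey without a request to withdraw is missing data for that timepoint and not withdrawal. Amend the presumed-withdrawal sentence in 3.3.1 and the survey-failure clause in 3.3.2 to match, and say how a partly completed 8-week survey counts.
- Send the 6-month survey to every randomised woman who was eligible on the 8-week chart review and has not asked to withdraw.
- Leave the other removal criteria in 3.3.1, including the intake-survey criterion, as they are for the purpose of this edit.
- Align Section 13.0 for a woman who answers at 6 months but missed the 8-week survey.
- State separately who is analysed at 6 months. The edits above settle only who is asked.

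The cost is wording in four sections, one REDCap send rule, ethics review of the amendment, and some low-yield emails. Whether the consent form needs a matching change cannot be judged, because the consent pages are not in the public copy. The change should be in place before the first 6-month emails go out.

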7.3 Duration of Participation

Patients will participate in this study for approximately 10 months. Routine prenatal care necessitates a visit between 24- and 28-weeks gestation, which is the recruitment visit. Most women will deliver between 37- and 42-weeks gestation, and there will be questionnaires sent at 8 weeks and 6 months after delivery. The 8-week questionnaire is the primary endpoint for patient participation in this study.

8.0 Subject Numbers and Statistical Plan

8.1 Number of Subjects

A sample size of 100 participants per group (200 total) will provide us with a sufficient sample size. However, we anticipate 10% of the participants may drop-out prior to study completion; therefore, we will enroll of total of 224 participants.

8.2 Sample size determination

We used 80% power to detect a difference between the proportions of women using birth control at 8 weeks of 0.75 in the nutrition informational handout and 0.90 in the birth control information handout using a two-sided chi-square test having a significance level of 0.05.

8.3 Statistical methods

To determine the difference in postpartum contraception use at 8 weeks, a two-sided chi-square test will be used to compare the women between those who receive a contraception-specific handout and those that receive a nutrition-specific handout.

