1.2 Primary Study Endpoints

The primary study endpoint is contraception use at 8 weeks postpartum.

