4.2 Recruitment process

4.2. 1 How potential subjects will be recruited.

Patients will be approached in-person about participation in this study during their clinical visit.

4.2. 2 Where potential subjects will be recruited.

[name], [name] and [name] OB/Gyn offices.

4.2. 3 When potential subjects will be recruited.

During or after their 24-28-week pregnancy visit, which is a standard and pre-appointed visit during all pregnancies.

4.2. 4 Describe the eligibility screening process and indicate whether the screening process will occur before or after obtaining informed consent. Screening begins when the investigator obtains information about or from a prospective participant in order to determine their eligibility. In some studies, these procedures may not take place unless HIPAA Authorization is obtained OR a waiver of HIPAA Authorization when applicable for the screening procedures is approved by the IRB.

Patient schedules and medical records will be reviewed for eligibility prior to obtaining informed consent.

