7.2 Study Procedures

7.2.1 Timepoint 1: At 24-28 weeks gestation

At patients’ previously-scheduled prenatal appointment at 24-28 weeks gestational age, patients will receive a research-specific packet to include demographic questionnaire and proprietary questionnaire after determining the individual’s eligibility and obtaining informed consent. A cover letter will be provided to the patients briefly describing the study and their requested

participation. After obtaining proper consent and signing the necessary forms, patients will complete the demographic information found on the intake questionnaire in paper form. After completion of the initial demographic information (i.e. name, date of birth, email address, and mailing address), the patient will be randomized (randomization will be stratified by recruitment location) to either group A or B via REDCap and receive a sealed envelope containing the respective handout. The envelopes will simply be labeled “A” or “B” so that the study personnel are blinded to the allocation. The envelopes will be assembled by an individual outside of the study team who will determine the handout designations for A and B. A master copy of one sealed ‘A’ envelope and one sealed ‘B’ envelope will be provided to the statisticians; these envelopes will be opened at the end of the study to unblind the groups. Following randomization, the patient will receive her intake questionnaire with her demographic information already filled in to be completed during this visit. The completed intake questionnaire will then be returned and stored in a locked and secured location. These survey results will be compiled, entered, and stored under the Redcap database.

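### Randomisation is stratified by office but the primary chi-square ignores office: valid and adequately powered, with a little power given up if contraception use differs between offices

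*Combined protocol and SAP*

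**What the plan says.** - **Endpoint (1.2).** "The primary study endpoint is contraception use at 8 weeks postpartum", a yes/no outcome.
- **Randomisation (7.2.1).** "randomization will be stratified by recruitment location", done through REDCap. Section 4.2.2 lists three offices. No block size is given.
- **Sample size (8.1, 8.2).** 100 women per group are needed. The planned rates are "0.75 in the nutrition informational handout and 0.90 in the birth control information handout", with 80% power and a "two-sided chi-square test having a significance level of 0.05". Because "we anticipate 10% of the participants may drop-out prior to study completion", 224 are enrolled.
- **Analysis (8.3).** The section is one sentence: "a two-sided chi-square test will be used to compare the women between those who receive a contraception-specific handout" and those given the nutrition handout. It mentions no stratified test, no adjustment for location and no supportive analysis. Section 9.7, on statistical tests, is marked not applicable.

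Nothing elsewhere links the stratified randomisation to the analysis or says why location is left out.

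**The concern.** A factor is normally stratified on because it is expected to relate to outcome. Once the arms are balanced within office, differences between offices no longer add noise to the comparison of handouts. The pooled chi-square still counts them in its variance, so its standard error is too large. The test then rejects less often than 5% under the null and loses some power under the alternative.

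What is at stake is efficiency only. There is no added false-positive risk, and the planned power was calculated for this same pooled test using overall rates, so it does not depend on the offices being alike.

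**Working it through.** **1. The plan's own figures reproduce.** Inputs from 8.1 and 8.2: p1 = 0.75, p2 = 0.90, two-sided alpha 0.05, power 80%. The mean rate is 0.825.

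n per group = [1.960·√(2·0.825·0.175) + 0.842·√(0.75·0.25 + 0.90·0.10)]² / 0.15² = [1.053 + 0.443]² / 0.0225 ≈ 99.5, rounded up to 100.

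Power at 100 per group = Φ[(0.15·√100 − 1.053)/0.527] = Φ(0.848) = 80.2%. Allowing for 10% drop-out, 100/0.90 = 111.1, so 112 per group and 224 in all.

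**2. Why the pooled test becomes conservative.** Let the overall rate be 0.75, so the pooled variance per woman is 0.75·0.25 = 0.1875. With arms balanced within office, the share of that variance lying between offices, r, does not affect the treatment contrast. The true size of the pooled test is then about 2·[1 − Φ(1.960/√(1 − r))].

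Take offices with use of 90/60/45% and shares 60:20:20 (assumed). Between-office variance = 0.6·0.15² + 0.2·0.15² + 0.2·0.30² = 0.036, so r = 0.036/0.1875 = 0.192. The critical value becomes 1.960/√0.808 = 2.18, which gives a size of about 2.9%. For 85/65/55% the variance is 0.016, r = 0.085, and the size is about 4.0%. Both agree with the simulation below.

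**3. Simulation of size and power.** Overall rates were held at 0.75 and 0.90 with 100 evaluable women per arm, equal arms within each of three offices, and a common odds ratio across offices. There were 400,000 trials per row, with no continuity correction. Office rates and shares are assumptions.

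| Control use by office (shares) | Odds ratio | Size, pooled / CMH | Power, pooled / CMH | CMH gain, points |
|---|---|---|---|---|
| 75/75/75% | 3.00 | 4.9% / 4.9% | 81.6% / 81.3% | −0.3 |
| 80/70/65% (60:20:20) | 3.05 | 4.7% / 4.9% | 81.8% / 81.8% | 0.0 |
| 65/75/85% (equal) | 3.09 | 4.5% / 5.0% | 82.0% / 82.3% | +0.3 |
| 85/65/55% (60:20:20) | 3.23 | 4.0% / 4.9% | 82.4% / 83.8% | +1.4 |
| 55/75/95% (equal) | 3.38 | 3.4% / 4.9% | 82.8% / 85.0% | +2.2 |
| 90/60/45% (60:20:20) | 3.60 | 2.9% / 5.0% | 83.4% / 86.8% | +3.4 |

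The simulated 81.6% in the first row is slightly above the 80.2% in step 1, which is a normal approximation.

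**4. Two variations (60:20:20).**

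- *Random loss from 224 to about 200.* At 80/70/65%, power is 81.6% pooled and 81.8% CMH. At 90/60/45% it is 83.1% and 86.8%, a gain of 3.7 points, with pooled size 3.2%.
- *Allocation not blocked within office*, examined because block size is not stated. The pooled test has nominal size (5.0 to 5.1%). Power, pooled and CMH, is 81.2% and 80.6% with no office differences, 81.2% and 83.0% at 85/65/55%, and 81.3% and 86.1% at 90/60/45%. CMH therefore ranges from a loss of 0.6 to a gain of 4.8 points.

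**The case against.** The strongest reply is that nothing here is wrong. Sections 8.2 and 8.3 name the same test, that test is valid, and it keeps the planned power, so the choice is between two acceptable analyses. This stands, and it is why the point is minor.

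The benefit also depends on figures the plan does not give. With arms balanced within office, the gain passes one point only when offices differ by 30 points or more, and nothing in the documents suggests gaps that wide. The offices are in one health system and recruit under the same criteria. Section 15.2 sizes recruitment on a single office and adds the other two to help reach the target, so one office may dominate. With an assumed 80:10:10 split, power (pooled, then CMH) is 81.7% and 81.6% at 77/72/62%, and 82.1% and 82.9% at 80/60/50%. It takes 82.5/50/40% to gain 2.3 points. This too stands: the likely gain is small and may be nil.

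Finally, making CMH the primary test means 8.2 no longer names the primary test, and a supportive adjusted analysis would avoid that. It is a workable alternative. The mismatch has little consequence, however: even with no office differences, CMH has 81.3% power with balanced arms and 80.6% without blocking. The effect estimate with its interval is strictly a separate reporting gap, but it belongs in the same sentence.

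**Conclusion.** The concern holds as a minor, optional improvement. The plan stratifies by location and then does not use location. The pooled chi-square remains valid, its size is at or below about 5%, and its power exceeds 80% in every scenario examined.

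The trade-off favours the stratified test: a possible loss of 0.3 to 0.6 points if offices are alike, against a gain of about 1 to 3.5 points with balanced arms if they differ widely. The gain reaches 4.8 points only in the most extreme unblocked case shown. At modest differences the two tests are practically equal.

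These sizes assume 200 evaluable women, a common odds ratio across offices, the planned overall rates, and the office rates and shares stated. Drop-out above 10% is a separate question.

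**What to change.** In 8.3, before the groups are unblinded:

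- Make the primary test of contraception use at 8 weeks a two-sided Cochran-Mantel-Haenszel test at the 0.05 level, stratified by recruitment location.
- Report the Mantel-Haenszel risk difference with its 95% CI.
- Keep the unstratified chi-square as a sensitivity analysis.

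Leave the numbers in 8.1 and 8.2 unchanged. A short clause could note that the sample size was calculated for the unstratified test.

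The cost is about one sentence of wording. Location is already held in REDCap as the stratification variable, so no new data are needed. The only statistical price is the 0.3 to 0.6 points of power if the offices turn out not to differ.

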2.0 Background

2.1 Scientific Background and Gaps

Reducing unintended pregnancies and those that are conceived within 18 months of a previous livebirth is an important health concern in the United States. Both unintended and close-interval pregnancies constitute 40% and 35% of pregnancies in the United States respectively with some overlap between the two categories and are associated with adverse maternal and fetal outcomes.¹ A national survey found that 17.8% of women using 'less-effective' methods and 23% of women using no birth control became pregnant in ≤ 18 months.² Access to better contraception education could potentially decrease the proportion of unintended pregnancies and close-interval pregnancies. In addition to the health concerns, 58% of women in the US would like more information about contraceptive options, and organized handouts on birth control have been shown to contribute to the choice in birth control.^{3,4}

However, there has been conflicting evidence about which educational methods increase postpartum contraception use.⁵⁻⁸ Therefore, we propose a randomized controlled trial (RCT) that assesses whether a handout on contraception options increases postpartum birth control use. The control group would receive a nutrition handout, and the intervention group would receive a handout on birth control options in addition to each receiving the standard of care. We will also give pre- and post-natal questionnaires, covering patient satisfaction, intention to use birth control, and how often a provider discusses birth control options.

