20.0 Future Undetermined Research: Data and Specimen Banking

20.1 Data and/or specimens being stored

The following data will be collected: Name, age, medical history, pregnancy information, delivery information, surgical history, previous contraception use, desire for future children. Specimens will not be collected.

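### Section 8.3 plans only an unadjusted test of 8-week contraception use and leaves previous contraception use, a likely predictor the trial already collects, out of the comparison

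*Combined protocol and SAP*

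**What the plan says.** The whole analysis plan for the primary endpoint is in section 8.3: "a two-sided chi-square test will be used to compare the women between those who receive a contraception-specific handout and those that receive a nutrition-specific handout". It names no adjustment, stratification or subgroup. Section 7.2.1 stratifies the randomization by recruitment location and by nothing else.

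The trial nevertheless gathers information likely to bear on the outcome. Section 2.1 states: "We will also give pre- and post-natal questionnaires, covering patient satisfaction, intention to use birth control, and how often a provider discusses birth control options". Section 20.1 lists among the data to be collected "previous contraception use, desire for future children".

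The eligibility criteria in 3.1 and 3.2 do not refer to a woman's contraceptive plans or history, so the randomized groups will mix women with different prior likelihoods of using contraception.

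Section 8.2 sizes the trial on "0.75 in the nutrition informational handout and 0.90 in the birth control information handout", "using a two-sided chi-square test having a significance level of 0.05", with 80% power.

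On timing, section 7.2.1 has the woman give her identifying and contact details, be randomized and receive a sealed envelope, and only then complete the rest of the intake questionnaire.

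**The concern.** Whether a woman used contraception before is likely to predict whether she uses it 8 weeks after delivery. When a predictor of a binary outcome is available, a comparison made within its levels removes outcome variation that has nothing to do with the handout. An unadjusted test leaves that variation in.

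Two things are at stake. The first is power in a trial sized with almost no margin for an ambitious 15-point difference. The second is credibility: if the adjusted analysis is not written down before the groups are unblinded, any later use of these variables is post hoc.

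**Working it through.** **Inputs from the documents.** Two-sided chi-square at 0.05, 80% power, 0.75 v 0.90 (section 8.2); 100 per group, 10% drop-out, 224 enrolled (section 8.1).

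**Input not in the documents.** How strongly previous contraception use predicts 8-week use. It is varied below from weak to very strong.

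**1. The plan's own figure.** With pooled variance and no continuity correction,

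n = [1.96·√(2·p̄·(1−p̄)) + 0.8416·√(p₁(1−p₁) + p₂(1−p₂))]² / d²

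- p̄ = (0.75 + 0.90)/2 = 0.825, so 2 × 0.825 × 0.175 = 0.28875, with square root 0.5374.
- 0.75 × 0.25 + 0.90 × 0.10 = 0.2775, with square root 0.5268.
- n = (1.0532 + 0.4433)² / 0.15² = 2.2397 / 0.0225 = 99.5, rounded up to 100 per group.

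The formula power at 100 per group is 80.2%. For drop-out, 100/0.9 = 111.1, so 112 per group and 224 in all. Both figures reproduce.

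**2. What the effect requires.** A rise from 0.75 to 0.90 means that 0.15/0.25 = 60% of women who would otherwise not be users become users.

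**3. Gain from stratifying.** Simulation of 100 per group, with a two-level predictor and 60% conversion in each level, so that the overall rates stay at 0.75 and 0.90. For the moderate case:

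- control: 0.75 × 0.85 + 0.25 × 0.45 = 0.75;
- handout: 0.75 × 0.94 + 0.25 × 0.78 = 0.90.

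| Assumed predictor | Split of women | Control use by level | Unadjusted chi-square | Mantel-Haenszel |
|---|---|---|---|---|
| Weak | 70%/30% | 80% v 63% | 81.5% | 81.7% |
| Moderate | 75%/25% | 85% v 45% | 81.4% | 84.8% |
| Very strong | 75%/25% | 90% v 30% | 81.6% | 89.9% |

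Under no effect, both tests reject in about 5% of runs.

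**4. A different structure.** Suppose instead that a share of women have already decided and 95% of them use contraception, with the handout acting only on the rest. With the overall rates again 0.75 and 0.90, stratifying on that share moves simulated power from 81.5% to 82.2% if 20% are decided, and from 81.3% to 84.9% if 50% are. The gain is under 1 to about 4 points.

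**5. Precision of a subgroup.** In the moderate case the low-use level has about 25 women per group, with use of 0.45 v 0.78. The 95% half-width of the risk difference is 1.96 × √(0.45 × 0.55/25 + 0.78 × 0.22/25) = 1.96 × 0.129 = 0.25, or 25 points. The difference between the effects in the two levels is 0.33 − 0.09 = 0.24. Its standard error is √[(0.85 × 0.15 + 0.94 × 0.06)/75 + 0.01676] = 0.139, which gives about 41% power for the interaction.

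**6. Which variables are safe.** Previous contraception use is a past fact that the handout cannot change. Stated intention and desire for future children can change. Under 7.2.1 they may be answered with the envelope already in hand, so adjusting for them or splitting on them could bias a comparison that is otherwise protected by randomization.

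**The case against.** The best defence of the plan is that nothing in it is wrong. The chi-square is valid under randomization, matches the sample-size calculation, and answers the question in section 1.1, which is whether giving low-risk patients the handout raises use. All of that stands. The gain from adjustment is nil if the predictor is weak, and the very strong case is extreme. It is also fair to say that section 20.1 appears under storage for future research and does not place previous contraception use on the intake form. Section 3.3.1 names only identifying details, email address and obstetric history as key intake items. These points limit the size of the concern. They do not remove it, since adjustment cost no power in any case run and type I error held.

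A reader might go further and infer that enrolling women who have already made up their minds dilutes the effect, so that a null result could not be interpreted. If the 15 points held only among undecided women, with control use kept at 0.75, the overall difference would be 0.15 × (1 − s) for a decided share s. Power at 100 per group would then be 70%, 46% or 25% for s = 10%, 30% or 50%. The documents do not support that reading:

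- Section 8.2 states 0.75 and 0.90 for the handout groups as a whole, so any decided women are already inside those rates.
- No section gives the decided share.
- A 75% use rate at 8 weeks postpartum does not mean that 75% had decided by 24–28 weeks.
- A null result still has a plain meaning: offering the handout to this population did not detectably raise use.

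Adjustment would not undo dilution in any case, and a subgroup with an interval of ±25 points could not reliably explain a null result.

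**Conclusion.** The concern holds as a missed gain in precision, not as a flaw in validity. Section 8.3 makes no use of previous contraception use, which the trial collects. Under the design rates, using it would add between almost nothing and about 8 points of power, with about 3 points in the moderate case. This rests on the assumed strength of the predictor, on 60% conversion in each level, and on the item being available for nearly all women. The inference that the effect is diluted, or that a null result would be uninterpretable, is not established by the documents and is not part of this conclusion.

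**What to change.** In section 8.3:

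- Keep the chi-square as the unadjusted result.
- Pre-specify, before unblinding, an adjusted comparison of 8-week use by previous contraception use: Mantel-Haenszel, or logistic regression reported as a risk difference. Define the categories and say how a missing value is handled.
- State which of the two results carries the primary conclusion, so that it is not chosen afterwards. The power gain reaches the primary conclusion only if the adjusted result is the one named.
- Confirm that previous contraception use is asked at intake.
- Use desire for future children or intention, for adjustment or for a subgroup, only if these items are answered before the envelope is given. One way is to move them in 7.2.1 to the part of the form completed before randomization.
- Label any risk difference by intention as supportive and state its wide interval.

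The cost is a few lines in 8.3 and one more pre-specified model, with no added patients or visits. If intention or desire for future children is used, the intake form must also be reordered.
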